3.5.2. Treatment Group Assignment

After a screening period that is not to exceed 28 days (i.e. screening visit through baseline visit), patients who continue to meet entry criteria at the baseline visit will be randomized to one of the three treatment groups according to a computerized system.

Treatment assignments will be governed by a fixed randomization schedule designed to allocate patients between lorcaserin/metformin, lorcaserin, and placebo in a 1:1:1 ratio. Within each site, approximately equal numbers of patients will be assigned to each treatment group. Randomization will be stratified by site across each of the 2 sites.

3.5.3. Concomitant and Adjunctive Medications

Concomitant medications are allowed if at stable dose for at least 1 month prior to study entry and if they are not on the prohibited list of therapies. The addition of any medications during the study must be discussed with the PI. The use of these medications and the indication must be documented using the Other Medications Record (OMR) form.

3.5.4. Prohibited and Restricted Therapies During the Study

Pro-serotonergic drugs pose an increased risk of serotonin syndrome when taken together with lorcaserin. Prohibited pro-serotonergic drugs include meperidine, buspirone, dextromethorphan, triptans, tramadol, ritonavir, cabergoline, tryptophan, ginseng, St. John's wort. Treatment with insulin or any oral antihyperglycemic or hypoglycemic agent is not permitted. Certain drugs have

been found to increase metformin plasma or blood levels in healthy volunteers (furosemide, nifedipine, cimetidine) or present a theoretical risk of such an increase (cationic drugs). Cimetidine is a cationic drug that can raise metformin peak plasma levels by 60% in healthy controls, probably due to competition for shared renal tubular transport systems for elimination. Cimetidine and other cationic drugs (including amiloride, digoxin, morphine, procainamide, quinidine, quinine, ranitidine, triamterene, trimethoprim, or vancomycin) are permitted only with the permission of the Co-I ([name]) together with the PI ([name]). Furosemide and nifedipine can also increase peak plasma levels of metformin by 20% and require permission of Drs. [name] and [name].

3.5.4.1. Precautions

The patient's best medical interests should guide the Investigator in the management of conditions that are preexisting or that develop during the study (i.e., intercurrent illnesses or AEs). The use of all medications, for any indications, must be documented on the Other Medications Record (OMR). Medications that were given for any preexisting illness will be recorded on the Other Medications Record (OMR) at the Baseline Visit. Any changes to medications that are given for any preexisting conditions must be documented.

Patients should not undergo any elective medical procedure without prior consultation with the Investigator. An elective procedure (minor surgery, dental surgery, orthopedic surgery, etc.) that might require hospitalization or anesthesia should be deferred until after the study whenever clinically appropriate.

3.5.5. Discontinuation from Study Treatment

Study treatment MUST be immediately discontinued for the following reasons:

- Withdrawal of informed consent (subject's decision to withdraw for any reason) or if patient loses the ability to provide continued informed consent in the study
- Any clinical adverse event, clinical rating, laboratory abnormality or intercurrent illness which, in the opinion of the investigator, indicates that continued treatment with study therapy is not in the best interest of the subject
- Pregnancy
- Termination of the study

Study treatment must be reevaluated for the following reason:

- Brief Psychiatric Rating Scale total score increase by $\geq 20\%$ compared to baseline will trigger a clinical evaluation to include the site's PI. This may include the subject's regular mental health provider, as needed.

Pre-specified Discontinuation Criteria:

- 1) Subject has gained >7 kg compared to baseline weight (V0) at any visit
- 2) Subject is unwilling to continue taking study drug for any reason
- 3) Clinical Global Impression-Severity scale (CGI-S) score ≥ 6 or worsening of CGI-S score by ≥ 2 points compared to baseline
- 4) Evidence for new onset suicidal ideation, plan or evidence of self-harm based on Columbia Suicide Severity Rating Scale (C-SSRS)

- 5) eGFR <45 mL/min/1.73 m²
- 6) ALT, AST, GGT >2.5xULN (upper limit of normal), total bilirubin >1.3xULN
- 7) Serum CO₂ <19 mEq/L
- 8) Meets criteria for alcohol abuse or dependence

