3.8.1. Fasting Laboratory Visits

Patients must be fasting (i.e., at least 8 hours without caloric intake) for the Screening Visit and Visits 7 and 10 or Visit 52/discontinuation visit. Fasting laboratory tests are required for subjects to be randomized to study treatment. Study sites should call participants the day before study visits to remind them of the appointment and the need to fast. Fasting is not required for laboratory tests for Visit 13.

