3.8.9. Visit 7 (Week 12)

This visit will include completing:

- Vital Signs, weight
- Blood draw for laboratory assessment (LFT (AST, ALT, GGT, total bilirubin), creatinine, eGFR, Lipid Profile, HbA1C, fasting glucose)
- Study Medication Dispensing
- CGI-S
- BPRS
- C-SSRS

- Substance Use Scale
- Alcohol Use Questionnaire
- Other Medications Record
- Study Medication Adherence Form
- Adverse Events Form
- Behavioral Treatments and Behavioral Treatment Adherence Forms

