3.8.12. Visit 10 (Week 24)

This visit will include completing:

- Vital Signs, weight
- Study Medication Dispensing
- CGI-S
- BPRS

- C-SSRS
- Substance Use Scale
- Alcohol Use Questionnaire
- Other Medications Record
- Study Medication Adherence Form
- Adverse Events Form
- Behavioral Treatments and Behavioral Treatment Adherence Forms
- 24 hr food recall assessment, accelerometry
- EDE-Q (Eating Disorder Examination Questionnaire)
- TFEQ (Three-Factor Eating Questionnaire)
- FCI questionnaire (Food and Craving Inventory)
- Blood draw for laboratory assessment (chemistry, CBC w/diff, LFT (AST, ALT, GGT, total bilirubin), creatinine, eGFR, Lipid Profile, HbA1C, fasting glucose, insulin, leptin, Ghrelin, PYY3-36, GLP-1)
- Urine Drug Screen

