3.8.15. Visit 13 (Week 36)

This visit will include completing:

- Vital Signs, weight
- Study Medication Dispensing
- CGI-S
- BPRS
- C-SSRS
- Study Medication Adherence Form
- Other Medications Record
- Adverse Events Form
- Behavioral Treatments and Behavioral Treatment Adherence Forms

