3.8.20. Unscheduled Visits

Unscheduled visits may occur at any time during the study and may occur for many reasons. These visits require completion of the appropriate Unscheduled Visit form only if the visit occurs for one of the following reasons:

- Assessment of possible change in psychiatric symptoms
- Assessment of possible change in drug tolerability, adverse event
- Assessment of possible change in medical status
- Assessment of need for medication changes or adjustment

Forms available for these visits will include: CGI-S, Side Effect/Adverse Event Form, Vital signs, Alcohol Use Questionnaire, Substance Use Scale, Laboratory tests and/or Other Medication Record.

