3.9.10. Laboratory Test Assessments

Laboratory testing will be conducted at the respective medical center laboratories at the 2 sites for this study: UNC Hospitals and Columbia University Medical Center for the routine laboratory tests. Appetite regulatory hormone testing will be conducted in the UNC Endocrine Laboratory. These hormonal samples will be collected and stored locally at -80°C and then shipped in batches to the UNC Endocrine Laboratory at intervals over the course of the study. Blood will be drawn from each patient at the screening visit, and at the scheduled visits designated in the study Schedule of Events in Appendix 1 and Appendix 2. The following tests will be performed:

- Hematology: hemoglobin, hemoglobin A1C, hematocrit, RBC, WBC, differential white blood cell count, and absolute platelet count
- Serum chemistries: sodium, potassium, chloride, CO₂, BUN, creatinine, fasting glucose, AST, ALT, alkaline phosphatase, total protein, albumin, total bilirubin, estimated GFR
- Lipids: total cholesterol, LDL-C, HDL-C, triglycerides
- Hormonal assays: Fasting insulin, leptin, ghrelin, PYY3-36, GLP-1
- 2 Hour oral glucose tolerance test (2 hour OGTT)
- Urine screen for drugs of abuse
- Serum pregnancy test for women who can become pregnant must be performed at the Screening Visit.

Values outside the normal range will be assessed for clinical significance by the site PI. If the accuracy of the result is in question, the test(s) may be repeated. If the result of any test (or repeat test, if done) is indicated as clinically significant in the samples taken during the screening or baseline visits, the patient will NOT be randomized into the study without the permission of the PI. (Guidelines for identifying potentially clinically significant laboratory values will be provided).

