The results from this study are intended to be generalizable and therefore the inclusion/exclusion criteria are not restrictive with the exception of several specific safety issues. Patients must be overweight as defined by a BMI \geq 27. The study will allow any patient with schizophrenia or schizoaffective disorder who is not in the first-episode of illness. Concurrent affective illness, substance abuse (except alcohol abuse or dependence) and other axis I disorders are allowed. Patients can be on one or two antipsychotics, typical or atypical. Stable concurrent treatment with other classes of medications is allowed with the exception of monoamine oxidase inhibitor (MAOI) class of antidepressants, given the theoretical risk of developing serotonin syndrome for people taking lorcaserin. Enrollment will be limited to clinically stable outpatients. The most serious risk associated with metformin is lactic acidosis, a very rare but often fatal condition. The incidence is about 3 cases in 100,000 patient-years, with about 50% mortality when it occurs; however, in

more than 20,000 patient-years exposure to metformin in clinical trials, there are no known reports of fatalities.

Finally, the specific outcome measures were chosen primarily to assess the effects of metformin and lorcaserin on weight and selected metabolic parameters including measures of lipid and glucose metabolism. Additional outcomes will include effects on appetite regulatory hormones (e.g. leptin, grehlin, PYY3-36, and GLP-1), as well as information on appetite and feeding behavior (ie food intake assessments), fat distribution using DXA imaging, and accelerometry for assessing energy expenditure across the study. Evidence to support lorcaserin/metformin-associated benefits on measures of weight and lipid/glucose metabolism would provide generalizable information on a readily available weight-loss strategy for overweight patients with schizophrenia. Further assessments addressing mechanistic aspects of how metformin and lorcaserin may achieve weight loss will provide critical insights on how to design future studies using metformin and lorcaserin and also how to approach other novel interventions for antipsychotic weight gain.

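### Scheduled testing checks the serum CO₂ stopping rule only once before the final visit, at week 24

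*Combined protocol and SAP*

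**What the plan says.** Section 3.5.5 gives eight pre-specified discontinuation criteria. Criterion 5 is an eGFR limit, criterion 6 covers liver tests, and criterion 7 is "Serum CO₂ <19 mEq/L". The same analyte is used at entry, where a value below 20 excludes (3.2.2).

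Section 3.9.10 names CO₂ in one test group only: "Serum chemistries: sodium, potassium, chloride, CO₂, BUN, creatinine, fasting glucose" and further analytes.

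Appendices 1 and 2 mark the Chemistry row at screening, week 24 and week 52 (or earlier discontinuation). The visit lists agree with the tables:

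- Week 12 (3.8.9) has no chemistry panel: "Blood draw for laboratory assessment (LFT (AST, ALT, GGT, total bilirubin), creatinine, eGFR, Lipid Profile, HbA1C, fasting glucose".
- Week 24 (3.8.12) has it: "Blood draw for laboratory assessment (chemistry, CBC w/diff, LFT (AST, ALT, GGT, total bilirubin), creatinine, eGFR".
- Week 52 or discontinuation (3.8.19) has it.

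At week 36, Appendix 2 marks only the row for liver tests, creatinine and eGFR, and its footnote limits the liver tests to AST, ALT, GGT and total bilirubin. The visit list in 3.8.15 names no blood draw at all, yet 3.8.1 says "Fasting is not required for laboratory tests for Visit 13".

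Two other provisions bear on the point. Section 3.8.20 allows laboratory work at unscheduled visits ("Substance Use Scale, Laboratory tests and/or Other Medication Record"). Section 3.5.5 also requires drug to be stopped for any laboratory abnormality that the investigator judges to make further treatment unwise.

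**The concern.** A stopping limit protects subjects only when the value is measured. Section 8.2.1 describes the symptoms of lactic acidosis as mostly non-specific, so a low CO₂ without clear symptoms would be found mainly by scheduled testing. The schedule provides one such test before the final visit. The eGFR and liver criteria, listed just before it, are tested at weeks 12, 24 and 36.

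Section 8.2.1.2 speaks of monthly laboratory testing, but it names only renal and hepatic function, and the schedule of events shows no monthly tests of that kind. It does not supply the missing CO₂ values.

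The week-36 mismatch adds a practical risk. A site working from 3.8.15 alone could miss that draw altogether, including the eGFR and liver tests.

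What is at stake is safety monitoring. The primary weight comparison is not affected.

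**Working it through.** The plan states no figure here to reproduce. The check is a count of scheduled measurements, followed by simple interval arithmetic.

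**Scheduled tests, from Appendices 1 and 2**

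| Time | eGFR and liver tests | Chemistry (CO₂) |
|---|---|---|
| Screening (up to 28 days before baseline, so week −4 at the earliest) | yes | yes |
| Week 12 | yes | no |
| Week 24 | yes | yes |
| Week 36 | yes | no |
| Week 52 or discontinuation | yes | yes |

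Between randomization and the final visit there are 3 scheduled checks of criteria 5 and 6, and 1 of criterion 7.

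**Gaps between scheduled CO₂ values**

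- Now (weeks −4, 24, 52): 28 and 28 weeks.
- With CO₂ added at weeks 12 and 36: 16, 12, 12 and 16 weeks.

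**Time from metformin to the first CO₂ value.** Section 3.5.1 starts metformin at week 4 and puts the top dose step at week 8. It labels that step Visit 6, which the schedule places at week 10.

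- From the start of metformin: 24 − 4 = 20 weeks now; 12 − 4 = 8 weeks with the change.
- From the top step: 24 − 8 = 16 weeks now (24 − 10 = 14 if taken at Visit 6); 12 − 8 = 4 weeks with the change (or 12 − 10 = 2).

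**Mean wait to the next scheduled CO₂.** Assume a lasting, symptom-free fall below 19 that begins at a uniformly random time during the 48 weeks on metformin (weeks 4 to 52). The mean wait is the sum of the squared intervals divided by 2 × 48.

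- Now, intervals 20 and 28: (400 + 784)/96 = 12.3 weeks.
- With the change, intervals 8, 12, 12 and 16: (64 + 144 + 144 + 256)/96 = 6.3 weeks.

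**How many subjects this could touch.** The combination arm would hold 90/3 = 30 to 110/3 ≈ 37 subjects (3.2 and 7.2.1 give 90 and 110). Exposure is 30 × 48/52 = 27.7 to 37 × 48/52 = 34.2 patient-years. Section 4 gives the lactic acidosis rate: "The incidence is about 3 cases in 100,000 patient-years, with about 50% mortality when it occurs". Expected cases are 27.7 × 3/100,000 = 0.0008 to 34.2 × 3/100,000 = 0.0010.

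The documents give no rate for CO₂ below 19. If 1% to 5% of the combination arm crossed the limit (an assumption), that would be 0.01 × 30 = 0.3 to 0.05 × 37 = 1.9 subjects.

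**The case against.** The count itself is hard to dispute; the case against is about importance.

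- **No rule requires equal frequency.** The criteria already run on different clocks: CGI-S is rated at every visit, and the alcohol scales at weeks 4, 8, 12, 24, 32, 44 and 52. Section 8.2.1 asks for renal and hematologic tests at least once a year on metformin and names renal monitoring as the way to lower lactic acidosis risk. The eGFR schedule far exceeds that, and routine CO₂ is never named as the surveillance tool. This stands, and it is why the point is optional.
- **The wait figures describe an assumed event.** The protocol treats suspected lactic acidosis as an emergency, and a mean wait of 6.3 weeks would not catch a fast one. This also stands. The figures apply only to a slow, silent fall.
- **More tests bring more false stops.** Because the trial is blinded, all three arms would be tested, and about two-thirds of subjects never receive metformin. At the assumed 1% to 5%, 0.01 × 90 = 0.9 to 0.05 × 110 = 5.5 subjects could meet the criterion. Some would be well, and stopping them could cost week-52 weights in a trial sized on 27 per arm. This is a real cost, limited because 3.9.10 lets a doubtful result be repeated.
- **Laboratories may report CO₂ anyway.** Section 3.9.10 lists creatinine, eGFR, AST, ALT and total bilirubin in the same chemistry group. The documents cannot settle what a site would report, but the schedule keeps Chemistry as a separate row.

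None of these points supplies another scheduled CO₂ check.

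**Conclusion.** The concern holds, as a modest gap in safety monitoring. The CO₂ rule is not inoperative: unscheduled tests and the investigator's duty to stop drug remain, and the eligibility, renal, hepatic and alcohol rules are the main protection. The count and the intervals come straight from the schedule and need no assumption beyond the longest allowed screening window. The mean waits and the 1% to 5% crossing rate are illustrative only. Since lactic acidosis is so rare by the protocol's own figure, the argument for change is narrow: the sponsor has already written the rule, and it can be checked as often as the eGFR and liver rules at almost no cost. The missing draw in 3.8.15 is a separate inconsistency that should be corrected in any case.

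**What to change.** Add serum CO₂, or the whole chemistry panel, to the week-12 and week-36 draws in Appendices 1 and 2 and to the week-12 list in 3.8.9. In 3.8.15, first insert the missing week-36 draw (liver tests, creatinine, eGFR), then include CO₂ in it. The limit of 19 mEq/L can stay as it is.

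The cost is one analyte or a standard panel on samples already planned at two visits, plus edits to two tables and two visit lists. No draw is needed beyond those in Appendix 2. The downside is a small assay charge and some extra out-of-range values to review or repeat across all three arms, a few of which could stop drug in a well subject.

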3.5.6. Drug Supply and Administration

Study medication will be over encapsulated so that study assignment will not be known to subjects or clinicians.

3.5.6.1. Storage and Inventory Management

All study drugs will be stored in a secure, limited access area at controlled room temperature.

3.5.6.2. Accountability

The investigator, his/her designee or an investigational drug pharmacist must maintain an adequate record of the receipt and distribution of all trial supplies. Trial drug prescription, dispensing and compliance will be captured on the case report forms and will be source-validated by study monitors.

3.6. BEHAVIORAL TREATMENTS

A behavioral treatment aimed at modifying cardiovascular risk factors, including weight, activity level, blood sugar, blood pressure, and lipids will be provided to all study participants (see Appendix 9). This intervention will be provided by a trained clinician in individualized sessions at all study visits after the Baseline Visit. After the first two sessions, interim telephone calls will be made between study visits to each participant to reinforce elements of the program and to answer questions. The intervention will use the principles of “Behavioral Group-Based Treatment for Weight Reduction in Schizophrenia and Other Severe Mental Illnesses” developed by [name], and colleagues at the University of Pittsburgh. Nine individual sessions will each last approximately 30 minutes. A rating of adherence to the behavioral treatment program will be made using the Behavioral Treatment Adherence Record at each session. The topics of each session are as follows:

- Week 1: Self-monitoring: Awareness of Body Weight and What One Eats
- Week 2: Burning Calories by Exercise
- Week 3: Phone reinforcement
- Week 4: Controlling Urges to Overeat and Snack
- Week 5: Phone reinforcement
- Week 6: Burning calories by Using Energy
- Week 7: Phone reinforcement
- Week 8: Decreasing Food Cues to Overeat and Snack
- Week 9: Phone reinforcement
- Week 10: Developing good eating habits
- Week 11: Phone reinforcement
- Week 12: Self-control of overeating
- Week 14: Phone reinforcement
- Week 16: Changing snack habits

Week 18: Phone reinforcement
Week 20: Revisit Self-monitoring: Awareness of Body Weight and What One Eats
Week 22: Phone reinforcement
Week 24: Revisit Burning Calories by Exercise
Week 26: Phone reinforcement
Week 28: Revisit Controlling Urges to Overeat and Snack
Week 30: Phone reinforcement
Week 32: Revisit Burning calories by Using Energy
Week 34: Phone reinforcement
Week 36: Revisit Decreasing Food Cues to Overeat and Snack
Week 38: Phone reinforcement
Week 40: Revisit Developing good eating habits
Week 42: Phone reinforcement
Week 44: Revisit Self-control of overeating
Week 46: Phone reinforcement
Week 48: Revisit Changing Snack habits
Week 50: Phone reinforcement
Week 52: Increasing success

3.7. STUDY VISITS

Subjects will attend visits at least once a month at which structured assessments will be conducted according to the study Schedule of Events in Appendix 1 and Appendix 2. During the first two weeks of study treatment, all subjects will be assessed clinically at weekly Visits 1 and 2.

3.8. PROCEDURES BY VISIT

The required procedures and assessments for subject evaluation are outlined in the Schedule of Events in Appendix 1 and Appendix 2.

All investigator-rated scales must be performed by qualified clinicians. Every effort should be made to complete the required procedures and evaluations at the designated visits.

3.8.1. Fasting Laboratory Visits

Patients must be fasting (i.e., at least 8 hours without caloric intake) for the Screening Visit and Visits 7 and 10 or Visit 52/discontinuation visit. Fasting laboratory tests are required for subjects to be randomized to study treatment. Study sites should call participants the day before study visits to remind them of the appointment and the need to fast. Fasting is not required for laboratory tests for Visit 13.

3.8.2. Screening Visit

The purpose of the screening visit is to:

- Ensure that appropriate patients are entered into the trial;
- Determine that the patient meets eligibility criteria;
- Complete medical diagnosis screen
- Measure vital signs, height and weight
- Other Medications Record

- Measure metabolic parameters including fasting laboratories (i.e., lipid profile, glucose, Hemoglobin A1C, insulin, and lipids, 2 hour OGTT)
- Blood draw for laboratory assessment
- Urine drug screen
- Collect specified demographic and medical data
- Assess each subject's reliability and ability to participate in the ratings and the likelihood that the patient will follow the prescribed treatment regimen and protocol requirements;

Screening evaluations consist of:

- Informed consent: study explanation, questions answered, consent form signed
- Psychiatric diagnostic evaluation using SCID modules A-E;
- Verification that all inclusion/exclusion criteria are met (see Section 3.2.1 and 3.2.2), including confirmation of medication eligibility
- General clinical evaluation; physical exam and medical history (to include all events/conditions within the last 2 years and all events /conditions of clinical significance or relevance to the study)
- Clinical Global Impressions-Severity (CGI-S)

